### 8.3 Visit Schedule and Procedures

This will be an interventional, subject masked, bilateral, non-dispensing fitting study. Participants will be examined at two different points over the course of one day, V1 (lens dispensing), V2 (15 minutes post lens settling). Participants will wear two different pairs of lenses with **LENS A** fitted first to all participants, followed by **LENS B**. Anterior ocular health examination will be performed at baseline without the use of fluorescein.

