### 3 Study Hypothesis

### 3.1 Study Hypothesis

- Null hypothesis (Ho): There is no difference in clinical performance and subjective assessments between lens types.
- Alternative hypothesis (H1): There is a difference in clinical performance and subjective assessments between lens types.

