### 8.2 Study Materials

### 8.2.1 Contact lens

CooperVision will provide the site with an inventory of both study lenses (LENS A) and (LENS B) to allow participants to be fit with the lens powers available for this study.

All subjects will be trial fitted and, if suitable, dispensed the first pair of the assigned lens brand assigned per a determined table **assigned**. The lenses used in this study are all FDA approved and marketed products. Details of the study contact lenses are shown in Table1.

Brand	Biomedics ® 55 Evolution (LENS A)	Avaira Vitality™ (LENS B)	
Manufacturer	CooperVision Inc.	CooperVision Inc.	
Material	ocufilcon D	fanfilcon A	
WC %	55	55	
Base Curve (mm)	8.6	8.4	
Lens Diameter (mm)	14.2	14.2	
Sphere Power (D)	+ 6.00 to – 10.00 (0.50 steps after ± 6.00)	+ 6.00 to - 10.00 (0.50 steps after ± 6.00)	
Wearing schedule	Daily wear	Daily wear	

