### 8.2.6 Masking and Control of Study Materials

The contact lenses, (LENS A, and LENS B), will be masked to the subject only. The lenses will be removed from their blister pack by an assistant and transferred to an unmarked lens case to maintain the participants masked of the study lenses. Participants will then be instructed to remove the lenses from the lens case and insert them onto their eyes. It is not possible for the study investigators to be masked because of the need to follow the specific lens fitting guide during the lens prescription optimization visit.

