# The following outline identifies the two study visits and the general procedures, **and a state of the study and recorded in the case report forms**:

### 8.3.1 Visit 1: Baseline / Trial Fit / Lens order

- Subjects should attend this visit wearing their spectacle lenses.
- Explanation of the study.
- Sign informed consent form.
- Collect habitual sphere lens brand information.
  - o Brand
  - Power(s)
  - Replacement schedule (daily, 2-week, monthly)
- Anterior ocular health examination (Slit lamp without fluorescein).
- Insert trial LENS A
- Measure high contrast distance visual acuity and optimize the prescription if needed.
- Evaluate lens fit (
   lens fit acceptance)
- Order final LENS A.
- Remove LENS A and insert trial LENS B.

- Measure high contrast distance visual acuity and optimize the prescription if needed.
- Evaluate lens fit ( lens fit acceptance)
- Order final LENS B.

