### 8.3.5 Visit 4: 15 minutes (Evaluate LENS B / Study Exit)

•		
•	Lei	ns Fit Assessment
	$\blacktriangleright$	
	4	Overall fit acceptance $(0 - 4)^{\ddagger}$ and reason if Grade 2 or less.
	4	d
	4	Remove LENS B
	4	
	4	Complete the study exit form

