### 10 Statistical Analysis

### **10.1 Statistical analysis**

Summary statistics will be produced, (e.g., mean, standard deviation), by the principal investigator. Differences between lenses will be compared using Paired t-tests. Paired t-tests /analysis of variance for normal (interval/continuous) data, Wilcoxon's signed ranks test for non-normal (ordinal) data, chisquares test for nominal data. Comments regarding the clinical relevance of differences in subjective ratings will be based on the conclusion by Navascues-Cornago et al., Papas, et al. that on a scale of 0-100, differences greater or equal to 7 points would generally represent a difference that a patient would notice. Equivalence testing will be conducted for ratings of comfort, using Mintab 20.2. A value of - 7 and + 7 will be used as the margins for equivalence. Equivalence testing of visual acuity will be conducted using an equivalence margin of 0.10 logMAR.

A Binomial test will be used to evaluate lens preference questions. All participants who are evaluated in the study will be used in the analysis. In the event of missing data individual number of points will be excluded in the analysis and not extrapolated from the collected data. The critical alpha level for statistical significance will be set at  $p \le 0.05$ , with adjustment for multiple comparisons. Confidential

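### Every participant wears LENS A first and LENS B second, so no planned comparison can separate a lens difference from an order effect.

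*Combined protocol and SAP*

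**What the plan says.** All references are to the combined protocol and SAP.

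- **Hypothesis (Section 3.1).** The alternative is "There is a difference in clinical performance and subjective assessments between lens types".
- **Order (Section 8.3).** LENS A is "fitted first to all participants, followed by" LENS B. The visit outline agrees. At the Visit 1 trial fits the instruction is "Remove LENS A and insert trial LENS B". Visits 2 and 3 concern LENS A and Visit 3a concerns LENS B. The last step is headed "Visit 4: 15 minutes (Evaluate LENS B / Study Exit").
- **Assignment (Section 8.2.1).** Suitable subjects are "dispensed the first pair of the assigned lens brand assigned per a determined table". Text next to this phrase appears to be blanked. What can be read names no B-first group, and neither the synopsis nor Section 4 calls the study randomised or counterbalanced.
- **Masking (Sections 2 and 8.2.6).** The investigator rates the primary outcome, lens fit acceptance. Of the investigators the plan says "It is not possible for the study investigators to be masked".
- **Analysis (Section 10.1).** "Differences between lenses will be compared using Paired t-tests", with Wilcoxon's signed ranks test for ordinal data and equivalence tests for comfort and visual acuity. For preference, "A Binomial test will be used to evaluate lens preference questions". No period or sequence term is mentioned.

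**The concern.** A within-subject comparison of two lenses is a comparison of lenses only if wearing position is balanced or has no effect. Here position is fixed. Anything that changes between first and second wear is counted as a lens difference: grading drift in a rater who always scores A before B, a participant settling into the session, or a tendency to favour the lens worn last.

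A significant result could then be lens, order or both, and a null result could be a real lens difference cancelled by order. In the comfort and acuity equivalence tests, an order effect could create or hide equivalence. This cannot be repaired once the data are in. Because parts of the visit text are blanked, nothing is claimed here about the interval between lenses.

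**Working it through.** **1. Reproduce the plan's power.** Inputs from Section 10.2: SD of paired differences 0.83, difference 0.4, two-sided alpha 0.05. The noncentrality is difference / (SD/√n), with n − 1 degrees of freedom. At n = 40 the standard error is 0.83/√40 = 0.1312, the noncentrality is 0.4/0.1312 = 3.048 and the critical value is 2.023, giving power 0.8443. The plan's values at n = 36, 40 and 48 (0.802741, 0.844271, 0.904896) all reproduce. The sample-size arithmetic is sound for its inputs.

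**2. Show the aliasing.** Write each grade as subject level + lens effect (τ for B against A) + position effect (π for second against first) + error.

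- Under the fixed order, every difference B − A has mean τ + π. The columns for mean, position and lens have rank 2 for 3 parameters, so only the sum can be estimated.
- With both orders, B − A has mean τ + π in the A-first group and τ − π in the B-first group. The rank is 3. Half the sum of the two group means gives τ, and half their difference gives π.

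**3. Put assumed order effects into the planned test.** The documents give no value for π, so these are scenarios. Section 10.1 adjusts for multiple comparisons without saying how many, so alpha split over two and four tests is also shown, again as an assumption. Entries are rejection rates at n = 40 with no lens difference (τ = 0).

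| Order effect (grade) | Noncentrality | alpha 0.05 | alpha 0.025 | alpha 0.0125 |
|---|---|---|---|---|
| 0.05 | 0.381 | 6.6% | 3.5% | 1.9% |
| 0.1 | 0.762 | 11.5% | 6.8% | 3.9% |
| 0.2 | 1.524 | 32% | 22% | 15% |
| 0.3 | 2.286 | 61% | 49% | 38% |
| 0.4 | 3.048 | 84% | 76% | 67% |

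The last row equals the plan's whole detectable difference, so it is an extreme case.

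**4. Opposing order effect.** With a true lens difference of 0.4, the tested mean is 0.4 minus the order effect. For 0.1, 0.2 and 0.3 the remaining means are 0.3, 0.2 and 0.1, and power at alpha 0.05 is 61%, 32% and 11.5% instead of 84%.

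**5. Wilcoxon test.** This used 10,000 simulated trials with integer 0–4 grades from a rounded, clipped latent normal (assumed latent mean 3.0 or 2.5, correlation 0.3; SD of differences 0.80 to 0.84). Rejection is about 5% with no order effect, then about 12%, 32–34%, 62% and 85–87% for 0.1, 0.2, 0.3 and 0.4. Changing the test does not help.

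**6. Preference.** Assume 40 forced choices. The exact two-sided binomial test at 0.05 rejects at 13 or fewer, or 27 or more; its true size is 3.8%. If the lenses are equal but 60% or 65% favour the one worn last, it rejects 21% or 44% of the time.

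**7. The same quantities with both orders.** With a period term there are 38 degrees of freedom and the standard error is (0.83/2)·√(1/n₁ + 1/n₂).

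- 20/20 completers: 0.415·√(1/20 + 1/20) = 0.1312; power at 0.4 is 84.4%.
- 22/18 completers: 0.415·√(1/22 + 1/18) = 0.1319; power is 84.0%.
- Simulated type I error is 0.049 to 0.051 for additive order effects from 0 to 0.4 without carryover.
- Preference at 20/20, with 60% or 65% favouring the last-worn lens: the plain binomial test rejects 3.5% or 3.0%, and a Mainland-Gart/Fisher test 2.4% or 2.5%.

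**The case against.** The strongest objection is that no order effect of consequence has been shown. The primary outcome is a fit grade given by an investigator, not a sensation reported by the wearer. Participants are adapted wearers, both lenses are tried at Visit 1, and each is graded after the same 15 minutes. It is not obvious how 15 minutes in A would change the fit grade of B, and an order effect of 0.05 grade would lift the error rate only to 6.6%. Rater expectation attached to a particular lens would survive randomised order. These points stand as a reason to expect a small effect on fit. They do not cover rater drift between first and second gradings, nor the comfort and preference results.

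A second objection is that across the Visit 1 trial fits and the later wears the sequence is A-B-A-B, so lens is not collinear with a steady trend over the four occasions. That is correct, and such a trend could be explored. But first or second position within each session remains identical to lens, trial and ordered lenses may differ, and no such analysis is planned.

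Third, the table mentioned in Section 8.2.1 might vary the order. If it does, it contradicts Section 8.3 and the visit headings, and the protocol still needs correcting.

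Finally, the preference scenarios rest on assumptions, because the question and its response options cannot be seen. This limits the figures but not the aliasing.

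**Conclusion.** The concern holds. Lens and within-session position are completely aliased in the primary comparison and in every other planned between-lens comparison. That conclusion follows from the stated order alone and does not depend on any assumed effect size.

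The size of the resulting bias is unknown. The scenarios rest on the plan's SD of 0.83, 40 completers and an assumed additive order effect. They show that an effect of 0.1 grade, a quarter of the difference the trial is powered for, would more than double the nominal 5% error rate, and that 0.2 grade would raise it to 32%. These are not estimates of this trial's actual error.

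The change should be made before enrolment: the flaw cannot be corrected afterwards, it reaches the primary outcome, and preventing it costs almost nothing.

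**What to change.** - In Section 8.3, replace the single order with 1:1 randomisation to A-then-B or B-then-A, using permuted blocks, 22 per order among the 44 to be enrolled. Use each participant's allocated order at the Visit 1 trial fits as well, and reword the visit headings to match.
- In Section 8.2.1, say what the table is and make it agree with Section 8.3.
- In Section 10.1, analyse the 15-minute paired difference with a period term, and apply the same adjustment to the equivalence comparisons. Test preference with sequence taken into account, for example with a Mainland-Gart/Fisher test of preference by sequence.
- State the assumption: an additive period effect with no unequal carryover between the two orders.
- State the limit: randomised order does not remove lens-specific expectation in the unmasked investigator who grades the primary outcome.

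**Cost.** A randomisation list and new protocol and CRF wording, with no added visits, lenses or subjects. One degree of freedom is lost. Power at 0.4 is 84.4% with 20/20 completers and 84.0% with 22/18, against 84.4% now.

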# The following outline identifies the two study visits and the general procedures, **and a state of the study and recorded in the case report forms**:

### 8.3.1 Visit 1: Baseline / Trial Fit / Lens order

- Subjects should attend this visit wearing their spectacle lenses.
- Explanation of the study.
- Sign informed consent form.
- Collect habitual sphere lens brand information.
  - o Brand
  - Power(s)
  - Replacement schedule (daily, 2-week, monthly)
- Anterior ocular health examination (Slit lamp without fluorescein).
- Insert trial LENS A
- Measure high contrast distance visual acuity and optimize the prescription if needed.
- Evaluate lens fit (
   lens fit acceptance)
- Order final LENS A.
- Remove LENS A and insert trial LENS B.

- Measure high contrast distance visual acuity and optimize the prescription if needed.
- Evaluate lens fit ( lens fit acceptance)
- Order final LENS B.

### 8.3.2 Visit 2: Lens dispensing (Fit LENS A / Evaluate)

> Overall fit acceptance  $(0 - 4)^{\ddagger}$  and reason if Grade 2 or less.

### 8.3.3 Visit 3: 15 minutes (Evaluate LENS A)

•		
•	Ler	ns Fit Assessment
	$\succ$	Overall fit acceptance $(0 - 4)^{\ddagger}$ and reason if Grade 2 or less.
	≻	Remove LENS A
Vis	sit 3	a: Lens dispensing (Fit LENS B / Evaluate)
•		

### Confidential

8.3.4

### 8.3.5 Visit 4: 15 minutes (Evaluate LENS B / Study Exit)

•		
•	Lei	ns Fit Assessment
	$\blacktriangleright$	
	4	Overall fit acceptance $(0 - 4)^{\ddagger}$ and reason if Grade 2 or less.
	4	d
	4	Remove LENS B
	4	
	4	Complete the study exit form

### 9 Adverse Event Reporting

### 9.1 Adverse Response Definitions

Adverse Event (AE): An AE refers to any untoward medical occurrence (sign, symptom or disease) in a trial subject that does not necessarily have a causal relationship with the study device. AEs may be classified as 'unanticipated adverse device effects,' 'serious AEs,' 'significant AEs,' or 'non-significant AEs,' as defined below.

Classification	Definition
Serious Adverse Event	Those events that are life-threatening, or result in permanent impairment of a body function, or permanent damage to a body structure or necessitate medical (therapeutic) or surgical intervention to preclude permanent impairment of a body function or permanent damage to a body structure.

Unanticipated Adverse Device Effect	Adverse events in a clinical trial that were not previously identified in the protocol in terms of nature, severity, or degree of incidence. An Unanticipated Serious Adverse Device Effect is an unanticipated adverse event that is serious in nature and caused by or associated with the device and is considered reportable.
Significant Adverse Event	Those non-serious adverse events that occur with contact lens usage that are not sight-threatening but are usually symptomatic and may warrant therapeutic management and /or temporary or permanent discontinuation of contact lens wear.
Non-Significant Adverse Events	Those less severe non-serious adverse events that occur with contact lens usage that are not sight-threatening, may or may not be symptomatic and may warrant palliative management, such as ocular lubricants or temporary interruption of contact lens wear.

AE classification, coding (for reporting to the sponsor) and examples are provided in the following table of Contact LENS Adverse Event Classification and Reporting:

Code	Condition	Potential AE Classification	Reporting
01	Presumed infectious corneal ulcer	SERIOUS	
02	Permanent loss of ≥2 lines of best spectacle corrected visual acuity (BSCVA)	SERIOUS	
03	Corneal injury that results in permanent opacification within central cornea (6mm)	SERIOUS	Notify sponsor as
04	Neovascularization within the central 6mm of cornea	SERIOUS	soon as possible, within 24 hrs; IRB
05	Uveitis or Iritis	SERIOUS	reporting as per
06	Endophthalmitis	SERIOUS	requirements
07	Hyphema	SERIOUS	
08	Hypopyon	SERIOUS	
09	Persistent epithelial defect	SERIOUS	
00	Other serious event	SERIOUS	
11	Peripheral non-infectious ulcer (outside central 6mm)	SIGNIFICANT	Notify sponsor as
12	Symptomatic corneal infiltrative events	SIGNIFICANT	soon as possible,
13	Superior epithelial arcuate lesions (SEALs) involving epithelial split	SIGNIFICANT	within 5 working days; IRB reporting
14	Any temporary loss of ≥2 lines BSCVA for ≥2wks	SIGNIFICANT	as per
15	Corneal staining ≥ dense coalescent staining up to 2mm in diameter (i.e. moderate staining)	SIGNIFICANT	requirements

16	Corneal neovascularization ≥ 1.0mm to 1.5mm vessel penetration (if 2 Grade change from baseline)	SIGNIFICANT	
17	Any sign and/or symptom for which subject is administered therapeutic treatment or which necessitates discontinuation of lens wear for ≥ 2 weeks	SIGNIFICANT	
10	Other significant event	SIGNIFICANT	
21	Conjunctivitis: bacterial, viral, allergic	NON-SIGNIFICANT	
22	Papillary conjunctivitis if ≥ mild scattered papillae/follicles approximately 1mm in diameter (if 2 Grade change from baseline)	NON-SIGNIFICANT	
25	Asymptomatic corneal infiltrative events	NON-SIGNIFICANT	
26	Localized allergic reaction	NON-SIGNIFICANT	
27	Contact dermatitis	NON-SIGNIFICANT	
28	Any sign and/or symptom for which temporary lens discontinuation for > 1 day is recommended	NON-SIGNIFICANT	

### Normal or adaptive symptoms

Transient symptoms such as end-of-day dryness, LENS Awareness, itching or burning or other discomfort may occur with contact lens wear and may occasionally reduce wearing time. These are not reported as adverse events unless they are unexpected in nature, severity or rate of occurrence.

### 9.2 Procedures for Adverse Events

Treatment of an adverse event will depend on its nature and severity. Based on the clinical judgment of the investigator the subject may be referred to an ophthalmologist for treatment. The investigator will attempt to determine whether the reaction is related to the test device or a result of other factors.

An Adverse Event Form will be completed for each adverse event. If both eyes are involved, a separate Adverse Event Form will be completed for each eye. Whenever possible, the adverse event will be photo-documented.

Expenses incurred for medical treatment as part of study participation will be paid by the sponsor (bills and prescription receipts kept). The subject must be followed until resolution and a written report completed indicating the subsequent treatment and resolution of the condition.

### 9.3 Reporting Adverse Events

All potential Serious and Unanticipated Adverse Device Effects that are related or possibly related to subject participation in the investigation will be reported to the Principal Investigator and the sponsor within 24 hours of the investigator becoming aware of the event. The Principal Investigator will report the event to the EC/IRB as soon as possible (by fax, mail/delivery, phone, or email), but within 10 business days of becoming aware of the problem. All fatal or life threatening events will be reported immediately to the IRB.

Significant and Non-Significant Adverse Events will be reported to the sponsor as soon as possible, but no later than 5 working days after the occurrence.

Sponsor contact details are:

### 9.4 **Discontinuation from the Study**

All discontinuations will be fully documented on the appropriate CRF Exit and Adverse Event forms as needed. Participants will be followed until resolution (in most instances) and are free of the ophthalmic insert related complications or other ocular pathology. When possible study lenses involved in an Adverse Event will be returned to the sponsor in a new tightly sealed contact lens case and labeled with the subject identification and stored in Unisol non-preserved saline.

### 10 Statistical Analysis

### **10.1 Statistical analysis**

Summary statistics will be produced, (e.g., mean, standard deviation), by the principal investigator. Differences between lenses will be compared using Paired t-tests. Paired t-tests /analysis of variance for normal (interval/continuous) data, Wilcoxon's signed ranks test for non-normal (ordinal) data, chisquares test for nominal data. Comments regarding the clinical relevance of differences in subjective ratings will be based on the conclusion by Navascues-Cornago et al., Papas, et al. that on a scale of 0-100, differences greater or equal to 7 points would generally represent a difference that a patient would notice. Equivalence testing will be conducted for ratings of comfort, using Mintab 20.2. A value of - 7 and + 7 will be used as the margins for equivalence. Equivalence testing of visual acuity will be conducted using an equivalence margin of 0.10 logMAR.

A Binomial test will be used to evaluate lens preference questions. All participants who are evaluated in the study will be used in the analysis. In the event of missing data individual number of points will be excluded in the analysis and not extrapolated from the collected data. The critical alpha level for statistical significance will be set at  $p \le 0.05$ , with adjustment for multiple comparisons. Confidential

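### Section 10.1 names paired tests for interval and ordinal data but only a plain chi-square for nominal data, although every participant wears both lenses

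*Combined protocol and SAP*

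**What the plan says.** Section 10.1 of the combined protocol and SAP opens its comparison rule with "Differences between lenses will be compared using Paired t-tests" and then assigns tests by type of data. Interval data get the paired t-test or analysis of variance. Ordinal data get "Wilcoxon's signed ranks test for non-normal (ordinal) data". Nominal data get "chisquares test for nominal data", with no mention of McNemar or any other matched form here or elsewhere in the visible text. Preference has its own rule: "A Binomial test will be used to evaluate lens preference questions". The 5% significance level applies "with adjustment for multiple comparisons".

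Section 8.3 fixes the design: "Participants will wear two different pairs of lenses", Lens A first and Lens B second for everyone.

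The only nominal item visibly recorded per lens is the explanation attached to a low fit grade at Visits 2, 3 and 4 (sections 8.3.2, 8.3.3 and 8.3.5): "and reason if Grade 2 or less". Visit 1 (section 8.3.1) also collects habitual lens brand and replacement schedule, once per subject. Parts of the visit procedures are blacked out.

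**The concern.** Two of the tests listed by data type, the paired t-test and the signed-rank test, carry their pairing in their names. The third does not. An analyst who cross-tabulates lens by category and runs the usual Pearson chi-square would enter 40 people as 80 independent observations.

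The same eyes are assessed minutes apart, so positive correlation between a person's two responses is the likely case. The ordinary chi-square then overstates the variance of the between-lens difference, rejects too rarely when there is no difference, and misses real ones. In a study that also tests comfort and acuity for equivalence, an insensitive difference test on nominal items would lean towards reporting no difference. The form of the test should be fixed before the data are seen, since the text leaves the choice to whoever runs the analysis.

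**Working it through.** **1. The plan's own figure.** Section 10.2 gives 84% power for the primary rating (n = 40, difference 0.4, SD of paired differences 0.83, two-sided 5%). Noncentral t: noncentrality = (0.4 / 0.83) × √40 = 3.05 on 39 degrees of freedom, power 0.844. This matches Figure 1. It rests on the paired t-test and does not involve the nominal rule.

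**2. The two statistics.** For n pairs, let b and c be the two discordant counts, s₁ and s₂ the numbers positive on each lens (so s₁ − s₂ = b − c), and p̄ = (s₁ + s₂) / 2n.

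- Ordinary chi-square: (b − c)² / [2n p̄(1 − p̄)]
- McNemar: (b − c)² / (b + c)

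The numerators are equal. With equal rates p and within-subject correlation ρ, the variance of b − c is 2n p(1 − p)(1 − ρ), but the ordinary test uses 2n p(1 − p). Its statistic is therefore about (1 − ρ) times a chi-square on 1 df. At ρ = 0.5 the 5% cut-off of 3.84 acts like 3.84 / 0.5 = 7.68, a tail of about 0.6%. At ρ = 0.3 it acts like 3.84 / 0.7 = 5.49, about 1.9%.

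**3. Exact check.** Inputs from the documents: n = 40 and two-sided 5%. Rates and correlations are assumptions. All 12,341 paired 2×2 tables were enumerated and weighted by their multinomial probabilities, with P(both positive) = p₁p₂ + ρ√[p₁(1−p₁)p₂(1−p₂)].

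Rejection rate when the lenses do not differ:

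| Rates | ρ | Ordinary chi-square | McNemar, asymptotic | McNemar, mid-p |
|---|---|---|---|---|
| 50/50% | 0 | 5.7% | 5.3% | 4.6% |
| 50/50% | 0.5 | 0.7% | 4.3% | 4.1% |
| 70/70% | 0 | 4.8% | 5.0% | 4.7% |
| 70/70% | 0.3 | 1.9% | 4.3% | 4.3% |
| 70/70% | 0.5 | 0.6% | 4.4% | 3.9% |
| 90/90% | 0 | 5.9% | 4.6% | 3.6% |
| 90/90% | 0.5 | 1.0% | 3.9% | 1.4% |

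Power:

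| Rates | ρ | Ordinary chi-square | McNemar, asymptotic | McNemar, mid-p |
|---|---|---|---|---|
| 80 vs 60% | 0 | 0.497 | 0.496 | 0.482 |
| 80 vs 60% | 0.1 | 0.497 | 0.531 | 0.524 |
| 80 vs 60% | 0.3 | 0.496 | 0.625 | 0.624 |
| 80 vs 60% | 0.5 | 0.491 | 0.799 | 0.790 |
| 70 vs 60% | 0.3 | 0.110 | 0.183 | 0.182 |
| 70 vs 60% | 0.5 | 0.075 | 0.232 | 0.227 |
| 90 vs 80% | 0 | 0.247 | 0.213 | 0.211 |
| 90 vs 80% | 0.5 | 0.168 | 0.405 | 0.322 |

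At ρ = 0 to 0.1 all differences in power are under 4 percentage points, and some favour the ordinary test. If the multiplicity adjustment brought the level to 2.5% (assumed: Bonferroni over two items), power at 80 vs 60% and ρ = 0.5 would be 0.34 against 0.69.

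**4. How far the assumed correlation can go.** The largest ρ possible for 80 vs 60% is (0.60 − 0.48) / √(0.8 × 0.2 × 0.6 × 0.4) = 0.612. For 90 vs 70% it is (0.70 − 0.63) / √(0.9 × 0.1 × 0.7 × 0.3) = 0.509, so that pair of rates at ρ = 0.5 is almost at its limit and is left out of the table.

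**5. One table.** Take 31/40 positive on one lens and 24/40 on the other, with discordant pairs 8 and 1. Ordinary: p̄ = 55/80, statistic 49 / 17.19 = 2.85, p = 0.091. McNemar: 49 / 9 = 5.44, p = 0.020 (mid-p 0.021). The form of the test can decide the conclusion.

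**The case against.** The strongest reply is that the plan states no wrong test. McNemar's test is itself a chi-square test, the tests beside it are paired, and the paired form may well have been meant. That stands: a reader might infer that the plan commits to an unpaired analysis, and the text does not go that far. It is silent on the form, and its literal wording permits the unpaired one.

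Second, no affected analysis can be pointed to. The visible text names no nominal item as tested, and the blacked-out visit procedures can neither confirm nor exclude one. This stands too, and it is why the point is minor.

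Third, the fit explanation does not supply 40 complete pairs. It is recorded only at grade 2 or below, so a participant graded higher on either lens has no pair of explanations. It may also be purely descriptive. The 40-pair figures above therefore do not describe that item.

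Fourth, a blanket replacement of chi-square would be wrong for items such as habitual brand, which are recorded once per subject and form no Lens A by Lens B table. The fix is limited accordingly.

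A reader might also fear inflated false positives. In the settings computed with zero or positive correlation, the ordinary test stays at or below about 5.9%. Rates above about 6% arose only with negative correlation, which is not expected here.

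**Conclusion.** The point holds as an under-specification of minor severity. Read literally, section 10.1 allows an independent-samples test on paired nominal responses. The consequence is lost power, not false positives: hypothetically about 30 percentage points at 80 vs 60% with correlation 0.5 (0.49 against 0.80), about 13 at 0.3, and under 4 at 0 to 0.1. These sizes rest wholly on assumed rates and correlations, 40 complete pairs and two categories. Larger contrasts can be constructed near the mathematical limit of the correlation, but they should not be taken as the size of the problem.

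It would be wrong to infer that the trial's main result is at risk. The primary 0–4 rating, the sample size, the comfort and acuity equivalence tests and the binomial preference test do not use this rule.

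**What to change.** In section 10.1, replace the chi-square entry with:

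> For nominal items recorded once per lens, McNemar's test (asymptotic or mid-p, to be stated) for two categories and the Stuart-Maxwell test for more than two, on the within-subject Lens A by Lens B table. Chi-square only for nominal items recorded once per subject.

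If the fit explanation is to be tested and not just listed, add a category for no reason (grade above 2), so that every participant assessed with both lenses contributes a pair.

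The cost is one sentence. It needs no new data and no change to sample size or visits. If McNemar's test was already intended, the edit only makes that explicit.

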### 2 Study Objective

The aim of this non-dispensing fitting study is to evaluate the short term lens fit, vision performance and patient subjective experiences of the Biomedics® 55 Evolution sphere when compared to the Avaira Vitality™ sphere after 15 minutes of daily wear each.

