### The primary outcome variable is:

• Lens Fit Acceptance ratings (assessed by the investigator)

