### 10.2 Sample size

Using data from investigator's lens fit acceptance, collected in a previous study that evaluated soft contact lenses, a sample size was calculated (CooperVision data on file). Figure 1 shows the sample size calculation for a paired t-test in order to detect a difference between lenses in mean lens fit acceptance ratings.

Assuming a standard deviation of 0.83, and an alpha level of 0.05, a sample size of 40 subjects provides 84% power to detect a difference of 0.4 points on a 0 - 4 scale. The study will enroll 44 subjects with the aim to complete 40 in total.

Figure 1. Sample size calculation (Minitab 20.2. Statistics software)

Paired t Test
Testing mean paired difference = 0 (versus ≠ 0)
Calculating power for mean paired difference = difference
$\alpha$ = 0.05 Assumed standard deviation of paired differences = 0.83

Results			
Difference Sam	ple Size Targ	et Power Ac	tual Power
0.4	36	0.80	0.802741
0.4	40	0.84	0.844271
0.4	48	0.90	0.904896

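### Does the unspecified multiplicity adjustment in Section 10.1 undercut the 84% power claimed for the primary endpoint?

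*Combined protocol and SAP*

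**What the plan says.** The Protocol Synopsis and Section 2 name a single primary outcome, the investigator's rating of lens fit acceptance. Section 2 sets the comparison "after 15 minutes of daily wear each".

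Section 10.2 bases the sample size on that outcome alone: "Assuming a standard deviation of 0.83, and an alpha level of 0.05, a sample size of 40 subjects provides 84% power" to detect a 0.4-point difference on the 0–4 scale. Figure 1 shows a two-sided paired t-test with 0.83 as the standard deviation of the paired differences. On numbers, the section adds: "The study will enroll 44 subjects with the aim to complete 40 in total".

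Section 10.1 gives one general significance rule, p ≤ 0.05 "with adjustment for multiple comparisons". It also plans other inferential work:

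- comfort: "Equivalence testing will be conducted for ratings of comfort";
- visual acuity: "Equivalence testing of visual acuity will be conducted using an equivalence margin of 0.10 logMAR";
- preference: "A Binomial test will be used to evaluate lens preference questions".

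It does not name the adjustment method, list the tests covered, or say where the primary stands in relation to them.

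**The concern.** Read literally, the Section 10.1 rule covers every test in the study, the primary included. Most adjustments would then test the primary below 0.05, while Section 10.2 computes power at 0.05. Two things would be at stake.

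The first is power: 40 completers would give less than the stated 84%. The second is the decision rule. With neither method nor family fixed, a borderline primary result might be called significant or not depending on a choice made after the data are seen. The tests to be counted are real ones: two equivalence analyses and more than one preference question, besides fit acceptance.

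**Working it through.** **Inputs from the documents.** Difference δ = 0.4, standard deviation of paired differences σ = 0.83, two-sided α = 0.05, n = 40 completers, 44 enrolled (Section 10.2 and Figure 1).

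**Inputs not in the documents, assumed for illustration.** Bonferroni adjustment, primary inside a family of k tests, k = 2 to 5. Five would be fit, comfort, acuity and two preference questions. All figures assume the paired t-test of Figure 1. Section 10.1 also allows a Wilcoxon signed-rank test for ordinal data, for which the thresholds below would differ.

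**Formula.** Power = P(|T| > t_crit), where t_crit is the 1 − α/2 quantile of t on n − 1 degrees of freedom and T is noncentral t with the same degrees of freedom and noncentrality δ√n/σ. At n = 40 the noncentrality is 0.4 × √40 / 0.83 = 3.048.

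**Step 1: the plan's own figures.** At α = 0.05 the formula gives 0.802741 (n = 36), 0.844271 (n = 40) and 0.904896 (n = 48). All three match Figure 1 to six decimals. The 84% is therefore correct for a test at the full two-sided 0.05.

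**Step 2: power if the primary shared alpha (α = 0.05/k).**

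| k | α | n = 40 | n = 44 |
|---|---|---|---|
| 1 | 0.05 | 84.4% | 87.8% |
| 2 | 0.025 | 76.0% | 80.5% |
| 3 | 0.0167 | 70.6% | 75.7% |
| 4 | 0.0125 | 66.6% | 72.0% |
| 5 | 0.01 | 63.4% | 69.0% |

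At 40 completers the loss runs from 84.4 − 76.0 = 8.4 points (k = 2) to 84.4 − 63.4 = 21.0 points (k = 5).

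**Step 3: the borderline case.** The standard error at n = 40 is 0.83/√40 = 0.1312. The smallest significant observed difference is t_crit times this:

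- k = 1: 2.0227 × 0.1312 = 0.27
- k = 2: 2.3313 × 0.1312 = 0.31
- k = 5: 2.7079 × 0.1312 = 0.36

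An observed difference of 0.30 gives t = 0.30/0.1312 = 2.286 and p = 0.028 on 39 degrees of freedom. That passes 0.05 and fails a Bonferroni 0.025. Under Holm with two tests it still passes if the other p-value is at or below 0.025. So a shared family does not by itself settle the call; the method matters too.

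**Step 4: which reading the documents support.**

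- One primary outcome, compared once between lenses, creates no multiplicity on its own.
- Section 10.2 is the text specific to that outcome, and it uses 0.05. Section 10.1 is general and covers several kinds of outcome and test.
- Putting the primary first in a fixed sequence is also a multiplicity adjustment, and it too tests the primary at 0.05.
- Fit is graded at several visits (Sections 8.3.1 to 8.3.5), but the 15-minute objective in Section 2 points to one contrast: LENS A at Visit 3 against LENS B at Visit 4.

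Testing the primary at the full 0.05 makes Sections 10.1 and 10.2 agree. Placing it in a Bonferroni family makes them disagree, and nothing in the text calls for that.

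**The case for a change.** The best case for a change is that convention is not pre-specification. The Section 10.1 rule is the only decision rule in the document, and its wording does not exempt the primary. Section 3.1 puts clinical performance and subjective assessments under one null hypothesis, so it does not set the primary apart either. The investigators are unmasked (Section 8.2.6), an investigator assigns the primary rating, and the principal investigator produces the summary statistics (Section 10.1). Those are conditions in which a fully written rule is worth more. If alpha were shared, four extra subjects would not restore 84%: even with all 44 completing, two tests under Bonferroni give 80.5%.

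Part of this stands. The method and the set of tests for the non-primary comparisons are not written down, and the report will have to state both. How many such tests there are cannot be judged from the public text, because assessment items are blanked out in the visit schedule.

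What does not stand is a conflict over the primary. The power loss needs the primary to be in the family and a method that lowers its alpha, and the documents state neither. The two equivalence analyses also have a different null hypothesis from the primary difference test, and nothing says they form one family with it.

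**Conclusion.** No change is needed. The 84% is the correct power for a single primary comparison at two-sided 0.05, which is the reading that the one named primary outcome and its dedicated sample-size calculation support. It holds equally if the primary comes first in a fixed sequence. The lower figures, 76.0% to 63.4% at 40 completers, describe Bonferroni families of two to five tests that include the primary, which the plan does not set up.

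What remains is a gap in detail about the secondary comparisons. An analyst would test fit acceptance at 0.05 and apply a recognised adjustment such as Holm to the rest. The sample size rests on the primary alone, so the choice made for the rest does not touch the stated power. Writing this down would record the reading already implied and leave the primary test and the enrolment as they are. The conclusion assumes that the primary contrast is the single 15-minute comparison and that it is analysed by the paired t-test used in Figure 1.
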